5.13.5 Monitoring and Management of Adrenal Insufficiency and Hypophysitis

Adrenal insufficiency and hypophysitis have been observed in patients receiving NKTR-214 and nivolumab. Consider prompt evaluation when patients have signs or symptoms of hypophysitis or adrenal insufficiency which includes levels of early-morning adrenocorticotropic hormone, cortisol, thyroid stimulating hormone (TSH), and free thyroxine (T4). Co-management with an endocrinologist is recommended for patients with pre-existing adrenal insufficiency.

5.13.6 Monitoring and Management of Eosinophilia

5.13.6.1 NKTR-214-induced Eosinophilia

Frequent and significant eosinophilia has been observed in patients receiving NKTR-214, primarily starting at Cycle 2 with levels plateauing after Cycle 3, consistent with the known pharmacodynamic effect of IL-2 therapy. The eosinophilia pattern demonstrates a cyclic waxing and waning pattern whereby eosinophil levels peak approximately 7 days after each infusion and wane before the patient's next infusion. Isolated cases of hypereosinophilic syndrome and other eosinophilic disorders have been reported.

Absolute eosinophil count (AEC) should be closely monitored per protocol. If a study patient is suspected to have eosinophilic disorder (symptoms may involve skin, lungs, digestive tract, heart, blood, and nervous systems) with AEC at or above the 5000/ μ L (5×10^9 /L) level, delaying NKTR-214 treatment may be considered while evaluating and treating the patient as clinically indicated.

5.13.6.2 Eosinophilic Disorders

Isolated cases of hypereosinophilic syndrome and drug reaction with eosinophilia and systemic symptoms have been reported. If there is clinical concern for an eosinophilic disorder, the Investigator is encouraged to contact the Medical Monitor.

Additional details regarding eosinophilia and eosinophilic disorders are provided in the NKTR-214 Investigator's Brochure.

5.13.7 Criteria to Resume NKTR-214 and/or Nivolumab

Patients will be permitted to resume study drug(s) at the same dose level(s) following resolution of an AE to Grade \leq 1 or to baseline within 8 weeks after the last dose unless the Medical Monitor is consulted and agrees with the rationale for resuming therapy after 8 weeks, and with the exception of patients who meet criteria for permanent discontinuation as specified in Section 5.14.1.1. If patients required steroids to treat an AE, the taper must be completed and dose should be $<$ 10 mg prednisone per day. Patients who meet criteria for permanent discontinuation must not receive further study therapy.

Patients may resume treatment with study treatment when the drug-related AE(s) resolve to Grade \leq 1 or baseline value, with the following exceptions:

- Patients who delayed dosing for acute infection requiring systemic antibiotic therapy must be free of signs or symptoms of infection for 72 hours after completion of antibiotic therapy prior to resuming study treatment.
- Patients may resume study treatment in the presence of Grade 2 fatigue
- Patients who have not experienced a Grade 3 drug-related skin AE may resume study treatment in the presence of Grade 2 skin toxicity
- For patients with Grade 2 AST, ALT, and/or total bilirubin abnormalities, dosing may resume when laboratory values return to baseline and management with corticosteroids, if needed, is complete.
- Drug-related pulmonary toxicity, diarrhea, or colitis must have resolved to baseline before treatment is resumed. Patients with persistent Grade 1 pneumonitis after completion of a steroid taper over at least 1 month may be eligible for retreatment if discussed with and approved by the Medical Monitor.
- Drug-related endocrinopathies adequately controlled with only physiologic hormone replacement may resume treatment after consultation with the Medical Monitor. Grade ≥ 3 adrenal insufficiency or Grade ≥ 4 hypophysitis require discontinuation regardless of control with hormone replacement (see Section 5.14.1 for permanent treatment discontinuation criteria). Hospitalization for diagnostic workup of adrenal insufficiency without severe symptoms should not require discontinuation.
- For patients who must delay study treatment due to Grade ≥ 2 creatinine increase due to a non-inflammatory cause (see Sections 5.13.1 and 5.13.2) delay retreatment with study drug for approximately 3 to 5 days. After the dosing delay, the patient may resume study drug treatment when serum creatinine has returned to Grade ≤ 1 , as assessed within 24 hours, or as soon as locally feasible, except where permanent discontinuation of study drug is required (see Section 5.14.1.1).

Dose delay of NKTR-214 combined with nivolumab that results in treatment delay of > 8 weeks requires treatment discontinuation, with exceptions as noted in Section 5.14.1.1. However, if the toxicity resolves to Grade ≤ 1 or baseline > 8 weeks after the last dose, but the patient does not otherwise meet the criteria for permanent discontinuation (see Section 5.14.1.1), and the Investigator believes that the patient is deriving clinical benefit, then the patient may be eligible to resume the study drug(s) following the approval of the Medical Monitor.

5.13.8 Management Algorithms for Immune-Mediated AEs and Cytokine Release Syndrome

5.13.8.1 Management Algorithms for Immune-Mediated AEs Associated with Immuno-Oncology Agents

Immuno-oncology agents are associated with AEs that can differ in severity and duration from AEs caused by other therapeutic classes. Nivolumab and NKTR-214 are considered immuno-oncology agents in this protocol. Early recognition and management of AEs associated

with immuno-oncology agents may mitigate severe toxicity. Management Algorithms including the use of systemic corticosteroids (see the nivolumab Investigator's Brochure) have been developed to assist Investigators in assessing and managing the following groups of AEs (including, but may not be limited to):

- Gastrointestinal
- Renal
- Pulmonary
- Hepatic
- Endocrinopathy
- Skin
- Neurological (see [Appendix 6](#))
- Myocarditis

5.13.8.2 Cytokine Release Syndrome

Events of CRS have been reported after NKTR-214 exposure (5 patients). The majority of CRS events reported in these trials were Grade 1 or Grade 2 and resolved. Two Grade 3 events of CRS were reported and resolved. These cases either co-reported IL-2 mediated symptoms or were confounded (i.e., infectious etiology).

CRS is a clinical diagnosis with a constellation of symptoms often characterized by fever, tachypnea, headache, tachycardia, hypotension, rash, and/or hypoxia caused by the release of cytokines. In addition, diarrhea and end organ dysfunction can be seen in CRS. Many of these symptoms overlap with known AEs seen in NKTR-214 and nivolumab combination therapy (i.e., pyrexia and hypotension). These symptoms may be seen in infusion reactions as well as other known syndromes, such as tumor lysis syndrome and macrophage activation syndrome.

Manifestations of infusion reactions are provided in Section [5.13.9](#).

For suspected cases of CRS Grade 3 or higher, the Investigator is encouraged to contact the Medical Monitor. An algorithm for CRS management is provided in [Appendix 7](#).

5.13.9 Treatment of NKTR-214 or Nivolumab-Related Infusion Reactions

Infusion reactions have been reported during infusions with NKTR-214 and nivolumab. If such a reaction were to occur with either the NKTR-214 or nivolumab infusion, it might manifest with fever, chills, rigors, headache, rash, pruritus, arthralgias, hypotension, hypertension, bronchospasm, or other allergic-like reactions. Infusion reactions should be graded as outlined below (consistent with Common Terminology Criteria for Adverse Events [CTCAE] v5.0 grading of infusion-related reaction; please also refer to Section [8.3](#)).

Treatment recommendations are provided below and may be modified based on local treatment standards and guidelines, as appropriate:

For **Grade 1** symptoms (mild reaction; infusion interruption not indicated; intervention not indicated):

- Remain at the bedside and monitor the patient until recovery from symptoms. The following prophylactic premedications are recommended for future infusions: diphenhydramine 50 mg (or equivalent) and/or acetaminophen/paracetamol 325 to 1000 mg at least 30 minutes before subsequent infusions. Subsequent infusions may be administered at a reduced rate (e.g., 50% of the original infusion rate).

For **Grade 2** symptoms (moderate reaction requires therapy or infusion interruption but responds promptly to symptomatic treatment [e.g., antihistamines, non-steroidal anti-inflammatory drugs, narcotics, corticosteroids, bronchodilators, IV fluids]; prophylactic medications indicated for ≤ 24 hours):

- Stop the NKTR-214 or nivolumab infusion, begin an IV infusion of normal saline, and treat the patient with diphenhydramine 50 mg IV (or equivalent) and/or acetaminophen/paracetamol 325 to 1000 mg; remain at the bedside and monitor the patient until resolution of symptoms. Corticosteroid and/or bronchodilator therapy may also be administered as appropriate. If the infusion is interrupted, then restart the infusion at 50% of the original infusion rate when symptoms resolve; if no further complications ensue after 30 minutes, the rate may be increased to 100% of the original infusion rate. If symptoms recur after restarting the NKTR-214 or nivolumab infusion, then no further drug will be administered at that visit. Administer diphenhydramine 50 mg IV, remain at the bedside, and monitor the patient until resolution of symptoms.
- For future infusions, the following prophylactic premedications are recommended: diphenhydramine 50 mg (or equivalent) and/or acetaminophen/paracetamol 325 to 1000 mg administered at least 30 minutes before the infusion. If necessary, corticosteroids (up to 25 mg of methylprednisolone or equivalent) may be used (see [Appendix 5](#) for corticosteroid dose equivalents). Subsequent infusions may be administered at a reduced rate (e.g., 50% of the original infusion rate).

For **Grade 3 or Grade 4** symptoms (severe reaction, Grade 3: prolonged [i.e., not rapidly responsive to symptomatic medication and/or brief interruption of infusion]; recurrence of symptoms following initial improvement; hospitalization indicated for other clinical sequelae [e.g., renal impairment, pulmonary infiltrates]. Grade 4: life-threatening; pressor or ventilatory support indicated):

- Immediately discontinue infusion of NKTR-214 or nivolumab. Begin an IV infusion of normal saline and treat the patient as follows: recommend bronchodilators, epinephrine 0.2 to 1 mg of a 1:1000 solution for subcutaneous administration or 0.1 to 0.25 mg of a 1:10,000 solution injected slowly for IV administration, and/or diphenhydramine 50 mg IV with

methylprednisolone 100 mg IV (or equivalent), as needed. NKTR-214 or nivolumab will be permanently discontinued. The patient should be monitored until the Investigator is comfortable that the symptoms will not recur. Investigators should follow their institutional guidelines for the treatment of anaphylaxis. Remain at the bedside and monitor the patient until recovery of the symptoms.

In case of late-occurring hypersensitivity symptoms (e.g., appearance of a localized or generalized pruritus within 1 week after treatment), symptomatic treatment may be given (e.g., oral antihistamine or corticosteroids).

5.13.10 Sunitinib or Cabozantinib Dosing-Delay Criteria

Sunitinib or cabozantinib dosing should be delayed for the following:

- If UPCR ≥ 2.0 [≥ 227 mg/mmol] urine dipstick protein $\geq 3+$, obtain 24-hour urine protein to determine if dosing should be delayed.
 - Dosing may proceed if 24-hour urine protein < 3 g.
 - Delay dosing if 24-hour urine protein ≥ 3 g (see Section 5.13.11 for criteria to resume).
 - Recurrent 24-hour urine protein ≥ 3 g after dose reduction requires study drug discontinuation (refer to Sections 5.14.1.2 and 5.14.1.3).
- Clinical manifestations of CHF
- LVEF $> 20\%$ but $< 50\%$ below baseline
- Any Grade 2 drug-related hemorrhage
- Any Grade 2 or 3 drug-related venous thrombosis requiring anticoagulation, with the following exception:
 - Any recurrent or worsening venous thromboembolic event after restarting sunitinib or cabozantinib will require discontinuation
- Any Grade 3 drug-related adverse event or Grade 3 drug-related laboratory abnormality (e.g., AST, ALT, total bilirubin) that persists for more than 1 week or worsens despite supportive care management, with the following exceptions:
 - Grade ≥ 2 drug-related arterial thromboembolic events, including cerebrovascular ischemia, cardiac ischemia, or peripheral or visceral arterial ischemia, require discontinuation.
 - Grade ≥ 3 drug-related hemorrhage requires discontinuation (Section 5.14.1.2).
 - Drug-related AST or ALT $> 8 \times$ ULN requires discontinuation (Section 5.14.1.2).

- Concurrent AST or ALT $> 3 \times$ ULN ($> 2 \times$ baseline AND $> 3 \times$ ULN for patients with baseline elevation) and total bilirubin $> 2 \times$ ULN ($> 2 \times$ baseline AND $> 2 \times$ ULN for patients with baseline elevation), consistent with potential drug-induced liver injury (see Section 8.10), requires discontinuation.
- Grade 3 drug-related amylase or lipase abnormalities that are not associated with symptoms or clinical manifestations of pancreatitis do not require dose delay. In such cases, more frequent monitoring (e.g., weekly) of amylase and lipase is recommended. If amylase or lipase worsens to Grade 4 severity or the patient develops symptoms or clinical manifestations of pancreatitis, dosing should be delayed.
- Sustained Grade 3 drug-related hypertension (systolic blood pressure ≥ 160 mm Hg or diastolic blood pressure ≥ 100 mm Hg). Note: Stopping or reducing the dose of sunitinib or cabozantinib is expected to cause a decrease in blood pressure. The treating physician should monitor the patient for hypotension and adjust the number and dose of antihypertensive medications accordingly.
- Grade 4 drug-related amylase or lipase abnormalities require dose delay. Patients should be monitored for development of symptoms or clinical manifestations of pancreatitis.
- Grade 4 drug-related electrolyte abnormalities require dose delay. Electrolyte correction with supplementation/appropriate management should be promptly initiated.
- Grade 4 drug-related neutropenia, lymphopenia, leukopenia, anemia, or thrombocytopenia
- Any adverse event, laboratory abnormality, or intercurrent illness which, in the judgment of the Investigator, warrants delaying sunitinib or cabozantinib dosing
- For patients scheduled for major surgery, including dental surgery which may impact bone healing, sunitinib or cabozantinib dosing should be delayed at least 28 days prior to scheduled surgery. The treating physician should use clinical judgment with regard to the risks and benefits of the planned surgical procedure if it is not possible to delay cabozantinib or sunitinib dosing for 28 days prior to the procedure. A delay of cabozantinib and sunitinib dosing of 5 to 7 days is recommended for healing for minor surgery.

As a general approach, all AEs related to sunitinib or cabozantinib should be managed with supportive care, when possible, at the earliest signs of toxicity. Calcium, magnesium, potassium, and phosphorus should be kept above the lower limits of the laboratory normal values. Please refer to the sunitinib or cabozantinib prescribing information for additional information regarding dose modifications and AE management.

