5.13 Dosage Modification

Every effort should be made to follow planned dosing schedules for all study drugs in both treatment arms. Study drug administration may be delayed or modified for toxicity as described below and must be discontinued as required by criteria described in Section 5.14.

Dose modification for NKTR-214 and nivolumab in Arm A may be considered independently based on Investigator assessment of relationship of a toxicity to each of the study drugs. If only one of the study drugs meets the criteria for dose delay, then administration of the other study drug may be continued or delayed at the discretion of the Investigator. Likewise, in the event that one of the study drugs in Arm A is permanently discontinued due to toxicities, the other can continue to be administered.

Patients who require delay of nivolumab or NKTR-214 should be re-evaluated weekly or more frequently if clinically indicated and should resume treatment with combination of NKTR-214 and nivolumab when retreatment criteria are met (Section 5.13.7). Immuno-oncology agents are associated with AEs that can differ in severity and duration from AEs caused by other therapeutic classes. NKTR-214 and nivolumab are considered an immuno-oncology agent in this protocol. Early recognition and management of AEs associated with immuno-oncology agents may mitigate severe toxicity.

For patients randomized to Arm A: NKTR-214 or nivolumab administration defines a scheduled nominal dosing visit (i.e., Cycle X Day 1, Cycle X Day 22). If a patient is assessed for an intended nominal dosing visit but study drug is not administered (e.g., due to an AE requiring dose delay, drug unavailable), any assessments performed during that visit should be recorded as “unscheduled.” When study drug administration resumes, all assessments should be performed as scheduled for the next nominal dosing visit (i.e., Cycle X Day 1 or Cycle X Day 22 Visit).

For patients randomized to Arm B: Cycle 1 Day 1 is defined by the date that the first dose of sunitinib or cabozantinib is administered. Within a cycle, missed doses of sunitinib should be skipped and not replaced. Scheduled Cycle X Day 1 and Cycle X Day 22 visits are fixed relative to Cycle 1 Day 1, regardless of dose delays. If drug dosing is delayed at the time of these scheduled visits (e.g., due to an AE requiring dose delay, drug unavailable), the cycle visit is not shifted and all assessments should be performed as scheduled.

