5.13.11 Criteria to Resume Sunitinib or Cabozantinib

Patients may resume treatment with sunitinib or cabozantinib when the drug-related AE(s) resolve to Grade ≤ 1 or baseline value, with the following exceptions:

- Patients may resume dosing in the presence of Grade 2 fatigue.

- Patients who delayed dosing due to 24-hour urine protein ≥ 3.0 g may resume dosing at one dose level reduction when UPCr < 2.0 [< 227 mg/mmol]. Repeat episodes of urine protein ≥ 3 g despite dose reductions require study drug discontinuation (refer to Section 5.14.1.2).
- Patients who delayed dosing due to Grade 3 hypertension may resume dosing at the same dose or at one dose level reduction, at the discretion of the Investigator, when hypertension has improved to Grade ≤ 2 .
- Patients who delayed dosing due to Grade 4 lipase or amylase abnormalities may resume dosing upon resolution to Grade ≤ 2 .
- Patients who develop a pulmonary embolism and/or DVT should have study treatment delayed until therapeutic anticoagulation is established. Treatment with sunitinib may be resumed in patients with pulmonary embolism or DVT if it is determined that the event is uncomplicated and that the patient is deriving clinical benefit from sunitinib treatment and that anticoagulation does not place them at a significant risk that outweighs the benefit of resuming treatment per discretion of the Investigator.
- Patients who delayed dosing due to \leq Grade 2 hemorrhage may resume dosing if bleeding is under control (recovered to at least Grade 1 level) and has a low risk of recurrence.
- Patients who delayed dosing due to major surgery should not resume sunitinib until complete wound healing has taken place. Following sunitinib resumption, patients should be monitored for wound dehiscence, wound infections, and other signs of impaired wound healing.

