5.14 Discontinuation Criteria

5.14.1 Discontinuation from Study Treatment

Patients MUST discontinue investigational product (and non-investigational product at the discretion of the Investigator) for any of the following reasons:

- Patient's request to stop study treatment. Patients who request to discontinue study treatment will remain in the study and must continue to be followed for protocol specified follow-up procedures. The only exception to this is when a patient specifically withdraws consent for further assessments or contact with him/her or persons previously authorized by patient to provide this information.
- 2 years since Cycle 1 Day 1 (Arm A only)
- Any clinical AE, laboratory abnormality, or intercurrent illness which, in the opinion of the Investigator, indicates that continued participation in the study is not in the best interest of the patient
- See additional study treatment discontinuation criteria specific to NKTR-214 and nivolumab (Section 5.14.1.1), sunitinib (Section 5.14.1.2), and cabozantinib (Section 5.14.1.3) due to AEs.
- Termination of the study by the Sponsor

- Loss of ability to freely provide consent through imprisonment or involuntarily incarceration for treatment of either a psychiatric or physical (e.g., infectious disease) illness. (Note: Under specific circumstances, a patient who has been imprisoned may be permitted to continue as a patient. Strict conditions apply and Sponsor approval is required.)
- Disease progression in the absence of clinical benefit as determined by the Investigator
- Occurrence of a clinically significant AE found to be unacceptable or nonresolution of a clinically significant AE for > 8 weeks
- Symptomatic deterioration in the absence of tumor progression per mRECIST 1.1.
- Noncompliance of the patient with protocol-mandated procedures based on the judgment and agreement of both the Investigator and Sponsor

If a patient has not progressed following discontinuation of study drug(s), every effort should be made to continue to obtain radiographic tumor assessments (until the patient has documented progression by both the BICR and Investigator's assessment or begins a subsequent anticancer therapy).

A patient may also be withdrawn from investigational product/study by the Sponsor, Regulatory Authorities, or IRBs/IECs.

Patients may choose to discontinue the study at any time, for any reason, and without prejudice to further treatment.

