5.14.1.2 Sunitinib Discontinuation Criteria

Treatment with sunitinib should be permanently discontinued for any of the following:

- Any requirement for more than 2 sunitinib dose reductions
- Any Grade drug-related arterial thrombosis
- Grade ≥ 3 drug-related hemorrhage or recurrent Grade 3 drug-related hemorrhage after dose reduction
- Grade 4 drug-related symptomatic venous thrombosis
- LVEF reduction $\geq 50\%$ from baseline
- Grade 4 drug-related cardiac toxicity
- Any other Grade ≥ 2 drug-related arterial or venous thromboembolic events including cerebrovascular ischemia, cardiac ischemia, or peripheral or visceral arterial ischemia
- Erythema multiforme, Stevens-Johnson syndrome, toxic epidermal necrolysis or necrotizing fasciitis
- Thrombotic microangiopathy
- Nephrotic syndrome or repeat episodes of urine protein ≥ 3 g despite dose reductions
- Angioedema due to hypersensitivity
- Two or more symptomatic episodes of hypertension despite modification of antihypertensive medication(s) and reduction of sunitinib dose
- Any drug-related LFT abnormality that meets the following criteria require discontinuation:
 - Treatment-emergent ALT or AST > 3 times ULN ($> 2 \times$ baseline AND $> 3 \times$ ULN for patients with baseline elevation)
 - Total bilirubin > 2 times ULN ($> 2 \times$ baseline AND $> 2 \times$ ULN for patients with baseline elevation) or clinical jaundice, without initial findings of cholestasis (e.g., elevated serum alkaline phosphatase) (see Section 8.10)
 - Sunitinib should be interrupted for Grade 3 or 4 drug-related hepatic adverse reactions and discontinued if there is no resolution within 7 days. Sunitinib should be permanently discontinued if a patient subsequently experiences Grade 3 or 4 changes in LFT or have other signs and symptoms of liver failure.
- Any dosing delay lasting > 8 weeks unless the Medical Monitor is consulted and agrees with the rationale for resuming therapy after a delay > 8 weeks. Note that tumor assessments should continue as per protocol even if dosing is delayed.
- Any adverse event, laboratory abnormality, or intercurrent illness which, in the judgment of the Investigator, presents a substantial clinical risk to the patient with continued sunitinib dosing.

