5.14.1.3 Cabozantinib Discontinuation Criteria

Permanently discontinue cabozantinib for patients with any of the following:

- Any requirement for more than 2 cabozantinib dose reductions (i.e., reduction to less than 20 mg)
- Acute myocardial infarction or new CVA event (including TIA) confirmed by imaging (DWI MRI preferred; refer to [Appendix 6](#))
- Any other Grade ≥ 2 drug-related arterial or venous thromboembolic events including cerebrovascular ischemia, cardiac ischemia, or peripheral or visceral arterial ischemia
- LVEF reduction $\geq 50\%$ from baseline
- Any Grade ≥ 3 hemorrhage
- Grade 4 hypertension or persistent Grade 3 hypertension despite optimal medical management and cabozantinib dose reduction
- Reversible posterior leukoencephalopathy syndrome
- Development of GI perforation or drug-related fistula
- Nephrotic syndrome or recurrent nephrotic range proteinuria (i.e., recurrent 24-hour urine protein ≥ 3 g after dose reduction)
- Any drug-related LFT abnormality that meets the following criteria requires discontinuation:
 - Treatment-emergent ALT or AST > 3 times ULN ($> 2 \times$ baseline AND $> 3 \times$ ULN for patients with baseline elevation)
 - Total bilirubin > 2 times ULN ($> 2 \times$ baseline AND $> 2 \times$ ULN for patients with baseline elevation) or clinical jaundice, without initial findings of cholestasis (e.g., elevated serum alkaline phosphatase) (see Section [8.10](#))
- Any Grade 4 drug-related adverse event or laboratory abnormality, with the following exceptions:
 - Grade 4 neutropenia ≤ 7 days
 - Grade 4 lymphopenia or leukopenia
 - Grade 4 amylase or lipase abnormalities that are not associated with symptoms or clinical manifestations of pancreatitis
 - Isolated Grade 4 electrolyte abnormalities that are not associated with clinical sequelae and are corrected with supplementation/appropriate management within 72 hours of their onset
- Any dosing delay lasting > 8 weeks unless the Medical Monitor is consulted and agrees with the rationale for resuming therapy after a delay > 8 weeks. Note that tumor assessments should continue as per protocol even if dosing is delayed.

- Any adverse event, laboratory abnormality, or intercurrent illness which, in the judgment of the Investigator, presents a substantial clinical risk to the patient with continued cabozantinib dosing.

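### Protocol Section 5.13.10 treats drug-related Grade 4 anemia and thrombocytopenia on cabozantinib as dose delays, but Section 5.14.1.3, which controls, requires permanent discontinuation for both

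*Protocol*

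**What the plan says.** Section 5.13.10 of the protocol opens with a lead-in that covers both TKIs: "Sunitinib or cabozantinib dosing should be delayed for the following". One of its bullets is "Grade 4 drug-related neutropenia, lymphopenia, leukopenia, anemia, or thrombocytopenia". That bullet does not separate the two drugs and does not refer to the discontinuation criteria.

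Section 5.13.11 sets the restart rule: "Patients may resume treatment with sunitinib or cabozantinib when the drug-related AE(s) resolve to Grade" 1 or lower, or to baseline, subject to listed exceptions. None of those exceptions concerns anemia or thrombocytopenia.

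Section 5.14.1.3 lists the reasons for stopping cabozantinib permanently. One is "Any Grade 4 drug-related adverse event or laboratory abnormality, with the following exceptions". The exceptions are neutropenia lasting no more than 7 days, lymphopenia or leukopenia, amylase or lipase abnormalities without clinical pancreatitis, and isolated electrolyte abnormalities without sequelae that are corrected within 72 hours.

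On precedence, the introduction to Section 5.13 says that study drug may be delayed or modified for toxicity but "must be discontinued as required by criteria described in Section 5.14". Section 5.14.1 says "Patients MUST discontinue investigational product" and sends the reader on to the drug-specific lists, "and cabozantinib (Section 5.14.1.3) due to AEs".

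The sunitinib list in Section 5.14.1.2 ("Treatment with sunitinib should be permanently discontinued for any of the following") contains no general Grade 4 rule and no hematologic stopping rule.

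**The concern.** The same two events on the same drug get two different instructions: hold and restart in one section, stop for good in another. The sections nearest the dosing decision are the ones that lead to a restart. A site that follows them could re-expose a patient to cabozantinib after a Grade 4 toxicity for which the protocol requires it to be stopped, and would record a protocol deviation in doing so. Management at onset is the same either way, because the drug is held. Only the later restart differs.

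**Working it through.** No formula applies. The check sets the five cytopenias in the 5.13.10 bullet against the exceptions in 5.14.1.3, for cabozantinib and drug-related Grade 4 events.

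| Event | 5.13.10 | 5.14.1.3 | Result |
|---|---|---|---|
| Lymphopenia | Delay | Excepted | Consistent |
| Leukopenia | Delay | Excepted | Consistent |
| Neutropenia | Delay | Excepted up to 7 days, then stop | Can be read in sequence; not a direct conflict |
| Anemia | Delay | Not excepted: permanent stop | Conflict |
| Thrombocytopenia | Delay | Not excepted: permanent stop | Conflict |

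Count: 5 − 2 (fully excepted) − 1 (excepted up to 7 days) = 2 in direct conflict.

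**Which rule applies.** Section 5.13 makes delay permissive and discontinuation under 5.14 mandatory, and 5.14.1.3 is an instruction that names cabozantinib. The permanent stop therefore governs. For sunitinib, 5.14.1.2 has nothing to override the delay, so the bullet is correct for that drug.

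**Could the bullet be only a first step before stopping?** The rest of 5.13.10 does not read that way:
- A fall in LVEF is a delay above 20% but below 50% from baseline. The stop in 5.14.1.3 starts at 50%.
- Drug-related hemorrhage is a delay at Grade 2. Section 5.13.10 itself says that Grade 3 or higher requires discontinuation.
- Arterial thromboembolic events, AST or ALT above 8 × ULN, potential drug-induced liver injury and recurrent proteinuria are also flagged there for discontinuation.

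A reader may fairly take an unflagged bullet to mean delay, then resume.

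**What the restart text adds.** Section 5.13.12.2 says that a patient on 40 mg of cabozantinib whose delayed toxicity meets the 5.13.11 criteria will resume at 20 mg. It cites 5.14.1.3 only for too many dose reductions and for recurrent proteinuria. The sunitinib counterpart, 5.13.12.1, tells the reader to check Section 5.14 whenever a reduction is considered; the cabozantinib section has no such general instruction. Arm A has the safeguard in two places: 5.13.1 qualifies the delay by reference to the discontinuation criteria, and 5.13.7 bars further study therapy for patients who meet them. Sections 5.13.10 and 5.13.11 have no equivalent.

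**Were the two exceptions left out of 5.14.1.3 by accident?** The Arm A list in 5.14.1.1 excepts the same three Grade 4 cytopenias, with the same 7-day limit for neutropenia, and also omits anemia and thrombocytopenia. That favors reading the omission as intended.

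**The case against.** The strongest reply is that the protocol already resolves the matter. Section 5.13 puts 5.14 above the delay rules, so there is one determinate answer for cabozantinib. The combined bullet is right for sunitinib, and holding cabozantinib is the right first action, so the entry might be called incomplete rather than wrong. This stands as far as precedence goes. It does not correct the bullet, which together with the resume rule still leads to the wrong later action.

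A second reply is that the Section 5.14.1 mandate is qualified: it leaves non-investigational product to the investigator's discretion, and cabozantinib is a marketed comparator. That qualification should be acknowledged. The precedence argument does not depend on it, because Section 5.13 refers to study drug and 5.14.1.3 names cabozantinib. Section 6.0 also discusses the sunitinib and cabozantinib strengths in introducing a table titled Investigational Products, although the table rows are redacted.

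A third reply is that such events are probably uncommon. Section 2.4.2 reports Grade 3 or 4 hematologic adverse events of any cause in 3% of cabozantinib patients in the first-line Phase 2 trial, and Grade 3 or 4 anemia in 6% in the trial of previously treated patients. Taking the extreme assumption that all 300 Arm B patients receive cabozantinib, these rates give 300 × 0.03 = 9 and 300 × 0.06 = 18 patients. Both counts include Grade 3 and events not related to drug; the second covers anemia only. They suggest small numbers, but they do not give the rate of drug-related Grade 4 anemia or thrombocytopenia, and the share of Arm B on cabozantinib is not stated.

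**Conclusion.** The inconsistency holds. For cabozantinib, the delay entry in 5.13.10 gives the wrong disposition for drug-related Grade 4 anemia and thrombocytopenia, 2 of the 5 cytopenias it lists; 5.14.1.3 controls and requires a permanent stop. The conclusion rests on the precedence sentence in Section 5.13 and on reading the exceptions in 5.14.1.3 as complete. If the sponsor in fact meant delay, 5.14.1.3 would need amending instead, so one of the two sections has to change.

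The point is minor. It concerns restart after recovery on one of the two control-arm drugs, in an unknown number of patients. ORR and OS are analyzed as randomized and are not affected, and no sample size, power or alpha figure changes.

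**What to change.** In 5.13.10, limit the Grade 4 anemia and thrombocytopenia delay to sunitinib, and state that on cabozantinib these events require discontinuation under 5.14.1.3. In 5.13.11, add the sentence that 5.13.7 already uses for Arm A, barring further study therapy once permanent-discontinuation criteria are met. The added sentence also covers cabozantinib patients whose Grade 4 neutropenia lasts beyond 7 days. The sentence alone would close the restart gap; the qualifier removes the wrong instruction at its source.

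The cost is amendment wording only: one qualifier and one sentence.
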